13.5 Analysis of Exploratory Endpoints

For patients who progress on trametinib and crossover to the combination arm clinical outcomes will be summarized. Response rate (CR+PR) will be estimated along with progression-free and overall survival from the start of combination therapy. Toxicity for the crossover patients will be reported by type, frequency and severity according to the NCI Common Toxicity Criteria.

Clinical response will be associated with Gnaq/11 mutational status using Wilcoxon rank sum test. An additional exploratory objective is to assess whether circulating tumor DNA can be detected. If so, these numeric data will be summarized by clinical response.

Using the 30 or more paired tumor biopsies collected on this study, associations between suppression specifically of p-ERK, AKT, Cyclin-D1, and response to treatment will be assessed using Fisher's exact test. Baseline and post-treatment status as well as changes will be reported. Assessment of apoptosis in the paired samples will be performed by caspase3 cleavage; changes will be assessed by a Wilcoxon signed rank test. These correlative studies will be considered exploratory in nature.

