1.3 Exploratory Objectives

- To assess clinical outcomes (response rate, progression-free and overall survival) with trametinib and GSK2141795 after progression on trametinib
- To assess toxicity with trametinib and GSK2141795 after progression on trametinib
- To correlate clinical outcome with Gnaq/11 mutational status
- To assess the pharmacodynamic effects of trametinib alone and with GSK2141795, and utilize whole-transcriptome and reverse phase protein array to identify markers of sensitivity and primary resistance to trametinib alone and with GSK2141795
- To assess for changes in circulating tumor DNA with therapy

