2.3 Study Rationale

2.3.1 Uveal Melanoma is Characterized by Activation of the MAPK Pathway Via Functionally Activating Mutations in Gnaq/11.

Whereas cutaneous melanoma is characterized by the presence of activating mutations in BRAF or NRAS in 50% and 20% of cases, respectively,⁴² leading to the constitutive activation of ERK1/2, such changes are rare in uveal melanoma (UM).^{43,44} Indeed, no BRAF mutations were identified in a total of 276 primary or secondary uveal melanoma screened samples (although such mutations have been identified in occasional uveal melanoma cell lines).⁴⁵ Despite the absence of these mutations, activation of the mitogen-activated protein kinase (MAPK) pathway in UM remains important in the development and progression of this disease.

[figure not shown]
Work by William Harbour⁴⁶ and Boris Bastian⁴⁷ has demonstrated the presence of a functionally activating Q209L mutation in guanine nucleotide-binding protein Q polypeptide (Gnaq), a heterotrimeric protein that couples cell surface 7-transmembrane domain receptors to intracellular signaling pathways such as the MAP kinase pathway in 45% to 50% of primary UMs.^{46,47} Of the primary UMs without a Gnaq mutation, greater than 50% carry a gain-of-function mutation in Gna11 that, like Gnaq, also encodes for a widely expressed G-protein alpha subunit.⁴⁸ These mutations are responsible for MAPK activation in the majority of primary UMs.

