2.4 Correlative Studies Background

2.4.1 Correlation of Treatment Response with Genetic Background

Whereas cutaneous melanoma is characterized by the presence of activating mutations in BRAF or NRAS in 60% and 20% of cases, respectively, leading to the constitutive activation of ERK1/2, such changes are rare in UM.^{43,44} Despite the absence of BRAF or NRAS mutations,⁴⁵ the MAPK pathway remains of importance in the pathophysiology of UM, and constitutive activation of MEK and ERK have been observed.^{45,56} Functionally activating mutations have been identified in codon 209 at Q209L of Gnaq in 45% to 50% of primary UMs which appears to account for MAPK activation in a significant proportion of tumors.^{46,47} Of the primary UMs without a Gnaq mutation (mut), greater than 50% carry a gain-of-function mutation in Gna11 that, like Gnaq, also encodes for a widely expressed G-protein alpha subunit and also results in MAPK activation. Gna11 is a paralog of Gnaq that is 90% identical and shares overlapping functions in mouse melanocytes.^{57,58} Gnaq/11 are genes that encode for q class G-protein α -subunits. G proteins are a family of heterotrimeric proteins ($G\alpha\beta\gamma$) coupled to cell surface, seven-transmembrane spanning receptors. Upon ligand binding to these receptors, the GDP bound to the $G\alpha$ subunit of $G\alpha\beta\gamma$ is exchanged for GTP, resulting in a conformational change and the subsequent dissociation of the $G\alpha$ from the $G\beta\gamma$ subunits. These two subunits are then able to regulate various second messengers. $G\alpha$ activation is terminated by a GTPase intrinsic to the $G\alpha$ subunit. The q class $G\alpha$ ($G_q\alpha$) mediates its activity

through stimulation of phospholipase C β , which cleaves phosphatidylinositol 4,5-bisphosphate (PIP2) to inositol triphosphate (IP3) and diacyl glycerol (DAG). DAG goes on to activate protein kinase C, which ultimately activates downstream pathways including the MAPK signaling pathway. These Gnaq/11 mutations are not associated with clinical, pathological, immunohistochemical, or genetic factors associated with advanced UM, and represent an early event in disease pathogenesis.⁴⁶

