We hypothesize that tumors that harbor a mutation in Gnaq/11 are more dependent upon MAPK and PI3K pathway signaling and will be more susceptible to MEK inhibition alone and in combination with AKT inhibition. To test this hypothesis, we will correlate clinical outcomes with mutation status. Tumor genotyping for Gnaq/11 will be performed for patients enrolled on this study at MSK or elsewhere. Genotyping can be performed retrospectively and will not delay patient enrollment. Analysis for Gnaq/11 will be performed using previously collected paraffin embedded tumor tissue; however, should previously collected tumor tissue be unavailable or insufficient for testing, a repeat biopsy will be requested but will not be mandatory for study participation.

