2.4.3 Assessment of Circulating Tumor DNA and Correlation with Treatment Response

It is now well established that human tumor cells, through a variety of physiologic events such as apoptosis, necrosis and secretion, release single and double stranded fragments of DNA into the circulation.^{59,60} These oligonucleotides, which can range in size from 70 to 21,000 base pairs, have been detected in plasma samples as circulating, cell-free, tumor-derived DNA (ctdDNA) in a variety of human cancers.⁵⁹ Interesting, ctdDNA share the specific genetic and epigenetic abnormalities as their tumor cell of origin, and thus, are readily distinguished from cell-free DNA derived from normal cells. Point mutations, methylation patterns, and microsatellite alterations have all been identified in ctdDNA and have the potential to function as biomarkers for both tumor burden and even treatment response.

As discussed above, 80% of uveal melanomas harbor mutations in GNAQ and GNA11.⁴⁹ These genetic alterations are found predominately at nucleotide position 626 on codon 209 and are the product of a missense mutation (i.e. *GNAQ*^{626A>T}, *GNAQ*^{626A>C}, and *GNA11*^{626A>T}), which results ultimately in glutamine being replaced by leucine or proline (i.e. GNAQ

Glu209Leu, GNA11 Glu209Leu, and GNAQ Glu209Pro). Recently, Madic and colleagues developed and validated a method using real-time PCR using bi-directional pyrophosphorolysis-activated polymerization (PAP) that detects and quantifies tumor specific GNAQ/GNA11 mutations in ctdDNA in patients with uveal melanoma.⁶¹ Activating mutations in GNAQ/GNA11 were detected in the plasma samples of 20 of 21 (95%) patients with metastatic uveal melanoma, while such ctdDNA was absent in 20 healthy donors. Interestingly, the level of ctdDNA strongly and significantly correlated with tumor burden as assessed by cross sectional imaging. This indicates that tumor volume is a major determinate of ctdDNA.

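### The Gnaq/11 objective concerns clinical outcome, but 13.5 plans only a rank-sum test on response, with coding and arm unspecified; PFS and OS by mutation status should be added

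*Combined protocol and SAP*

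**What the plan says.** The exploratory objective in 1.3 is "To correlate clinical outcome with Gnaq/11 mutational status". Section 2.4.1 hypothesises that mutant tumours are more susceptible to MEK inhibition, alone or with AKT inhibition, and continues: "To test this hypothesis, we will correlate clinical outcomes with mutation status". The Schema and the heading of 9.4.1 use the same broad term.

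The same list in 1.3 shows what the term covers for crossover patients: "To assess clinical outcomes (response rate, progression-free and overall survival) with trametinib and GSK2141795 after progression on trametinib". Section 13.5 carries all three outcomes through for those patients.

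For Gnaq/11, 13.5 has one sentence: "Clinical response will be associated with Gnaq/11 mutational status using Wilcoxon rank sum test". It does not give the coding of response, the significance level, the sidedness or any handling of treatment arm. Neither 13.4 nor 13.5 compares PFS or OS by mutation status. Section 13.5 closes its correlative analyses with "These correlative studies will be considered exploratory in nature".

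**The concern.** The stated analysis is narrower than the objective, and it uses an endpoint that carries little information here. Few patients are expected to be wild type and few to respond, so a comparison of response by status rests on a handful of patients. By contrast, 13.1 expects 76 PFS events in 80 patients, and those data are collected anyway.

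There are two risks. A non-significant result on response could be read as evidence against the mechanistic hypothesis in 2.4.1 when the test had little chance of supporting it. And with coding and arm left open, the choice could be made after the data are seen. No primary or secondary conclusion of the trial depends on this analysis.

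**Working it through.** **Inputs from the documents**

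- Mutation prevalence: 2.4.3 says "80% of uveal melanomas harbor mutations in GNAQ and GNA11", so about 20% are wild type. Section 2.4.1 says "Functionally activating mutations have been identified in codon 209 at Q209L of Gnaq in 45% to 50% of primary UMs", and 2.3 says "Of the primary UMs without a Gnaq mutation, greater than 50% carry a gain-of-function mutation in Gna11". The last two imply at least 0.45 + 0.5 × 0.55 = 72.5% to 0.50 + 0.5 × 0.50 = 75% mutant, so at most 25–27.5% wild type.
- Response to MEK inhibition: 7 of 46 = 15% in the prior selumetinib trial (2.3.3). This is not a declared planning rate for the present trial.
- Patients: 80 (13.1) or up to 60 (13.2). Arm B is closed. If it stopped at about 20 and Arm A goes to 40, the total is 60; 40 is Arm A alone.
- PFS: median 16 weeks on trametinib, 76 events in 80 patients (95%), design hazard ratio 0.56 (13.1). The prior trial's treatment hazard ratio was 0.46 (2.3.3).

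**Assumptions.** The documents give no mutant/wild-type effect on any endpoint. The hazard ratios 0.56 and 0.46 are borrowed for scale only. The 95% event share is carried over to smaller totals.

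**Step 1. The plan's own power figure.** Schoenfeld: power = Φ(√(d·p(1−p))·|ln HR| − z). With d = 76, p = 0.5, HR 0.56, one-sided 5%: √19 × 0.580 − 1.645 = 0.88, so power is 81%, against the stated 80%. It reproduces.

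**Step 2. Binary response (CR+PR), most extreme split.** Put all r responders among the m mutant patients and none among the w wild type. The tie-corrected Wilcoxon statistic (no continuity correction) is then z² = (N−1)·r·w / [m·(N−r)].

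| N | Wild type | Responders | z | Wilcoxon two-sided p | Fisher two-sided p |
|---|---|---|---|---|---|
| 40 | 8 | 6 | 1.31 | 0.19 | 0.32 |
| 60 | 12 | 9 | 1.61 | 0.11 | 0.18 |
| 80 | 16 | 12 | 1.87 | 0.062 | 0.11 |
| 80 | 20 | 12 | 2.16 | 0.031 | 0.031 |

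If Arm B contributes only 1 response in 20 (assumed), 60 patients have 7 responders, and p is 0.16 with 12 wild type and 0.09 with 16. At 80 patients with 16 wild type, the one-sided p is 0.031.

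Exact two-sided power with 20% wild type and true rates of 15% v 0% is under 1%, 2% and 9% at 40, 60 and 80 patients. With 18.75% v 0% (15% overall, all in mutants) it is 1%, 10% and 31%.

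**Step 3. Ordered response (PD < SD < PR).** PD by week 8 comes from exponential PFS with a mutant median of 16 weeks: 1 − 0.5^(8/16) = 29% in mutants, and 46% or 53% in wild type at HR 0.56 or 0.46. PR is 15% in mutants and 0–5% in wild type. Power is from 20,000 simulated trials, two-sided 5%.

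**Step 4. PFS.** Schoenfeld with p = 0.2. For 60 patients and 57 events: √(57 × 0.16) = 3.02. At HR 0.56, 3.02 × 0.580 − 1.96 = −0.21, or 42%. At HR 0.46, 3.02 × 0.777 − 1.96 = 0.38, or 65%.

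| N (wild type) | HR | Ordered response | PFS |
|---|---|---|---|
| 60 (12) | 0.56 | 24–30% | 42% |
| 60 (12) | 0.46 | 36–44% | 65% |
| 80 (16) | 0.56 | 31–40% | 52% |
| 80 (16) | 0.46 | 46–58% | 77% |

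With 40 patients (38 events), PFS power is 30% and 48%.

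**The case against.** The analysis is exploratory, and no decision hangs on it. The phrase in 1.3 that spells out response, PFS and OS belongs to the crossover objective, not this one, and the heading of 2.4.1 speaks of treatment response, so response is a legitimate measure of drug susceptibility. Section 13.6.2 classifies response in several categories, and 13.5 chooses Fisher's exact test for biomarker suppression against response. That contrast suggests an ordered response was meant for the Wilcoxon test, so the poor binary figures may not apply.

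Much of this stands. It limits the weight of the point and makes the ordered reading the more plausible one. It does not supply the missing PFS and OS analyses, the coding or the handling of arm.

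A reader might also infer that the planned test would return a null whatever the truth. The figures do not support that: ordered-category power is moderate, and even the binary test can reach 0.05 with 80 patients and 25% wild type, or one-sided with 80 patients and 20%. Sidedness is not stated. Nor do the figures show that PFS would settle the question, since at a hazard ratio of 0.56 its power is only 30–52% across 40 to 80 patients.

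**Conclusion.** The mismatch holds: the objective concerns clinical outcome, and the plan analyses response alone, with coding and arm unspecified. With about 20% wild type and 15% response, a two-sided binary test has low power, at most 10% at 40 or 60 patients and up to 31% at 80 in the most favourable case run. Ordered response has moderate power, and PFS is ahead of it by about 12–31 percentage points in the scenarios tabulated.

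The ranking rests on assumed effect sizes, exponential PFS, the prior trial's response rate and the carried-over event share. The absolute power figures would move with any of these. Under none of the layouts would a non-significant result count as evidence against the hypothesis in 2.4.1. The point is worth acting on because the remedy is cheap, but it touches only an exploratory objective.

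**What to change.** In 13.5, add Kaplan-Meier estimates of PFS and OS by Gnaq/11 status, with a log-rank test and a Cox hazard ratio with 95% confidence interval, stratified by or adjusted for treatment arm. Keep response as a supporting analysis: state that the Wilcoxon test uses ordered RECIST categories, and report CR+PR by status with exact 95% intervals. State that all of it is exploratory and that a non-significant result will not be taken as evidence against the hypothesis.

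The cost is a few sentences in 13.5 and a little more analysis on data already collected. Arm B will contribute few wild-type patients (about 4 if it closed at 20 with 20% wild type), so its stratum adds little information.

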In collaboration with investigators at the Institut Curie, Paris France, MSK, and/or Columbia, we propose to prospectively measure ctdDNA in patients with metastatic uveal melanoma. The primary objective is to describe the evolution of ctdDNA levels measured by PAP in plasma of patients under treatment for metastatic uveal melanoma. Additionally, we will evaluate the early changes of circulating tumor DNA levels as early indicator of efficiency or non-efficiency of treatment and correlate circulating DNA levels with tumor imaging of metastases. Patients on this study at MSK will be required to submit peripheral blood samples prior to treatment, at various time points on treatment, and at progression.

All patients will undergo blood collection on a monthly basis for analysis of circulating tumor DNA levels. Using a real-time PCR developed based on bi-directional pyrophosphorolysis-activated polymerization (bi-PAP) for the quantification of ctDNA using 3'blocked primer pairs specific for the 3 recurrent mutually exclusive mutations of G α subunits Gnaq and Gnal1, Madic et. al. have been able to detect and quantify circulating tumor DNA in metastatic UM patients.⁶¹ We will utilize this assay to measure circulating tumor DNA and correlate changes in DNA levels with response to treatment.

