Target lesions. All measurable lesions up to a maximum of 2 lesions per organ and 5 lesions in total, representative of all involved organs, should be identified as **target lesions** and recorded and measured at baseline. Target lesions should be selected on the basis of their size (lesions with the longest diameter), be representative of all involved organs, but in addition should be those that lend themselves to reproducible repeated measurements. It may be the case that, on occasion, the largest lesion does not lend itself to reproducible measurement in which circumstance the next largest lesion which can be measured reproducibly should be selected. A sum of the diameters (longest for non-nodal lesions, short axis for nodal lesions) for all target lesions will be calculated and reported as the baseline sum diameters. If lymph nodes are to be included in the sum, then only the short axis is added into the sum. The baseline sum diameters will be used as reference to further characterize any objective tumor regression in the measurable dimension of the disease.

Non-target lesions. All other lesions (or sites of disease) including any measurable lesions over and above the 5 target lesions should be identified as **non-target lesions** and should also be recorded at baseline. Measurements of these lesions are not required, but the presence, absence, or in rare cases unequivocal progression of each should be noted throughout follow-up.

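### Section 13.5 limits the ctDNA analysis to detection and a summary by clinical response, and omits the imaging-correlation and early-change analyses that sections 1.3 and 2.4.3 call for

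*Combined protocol and SAP*

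**What the plan says.** The aims and the analysis sit in different sections.

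- **Section 1.3 (objective):** "To assess for changes in circulating tumor DNA with therapy".
- **Section 2.4.3 (aims):** describe how ctDNA levels evolve on treatment, evaluate early changes as an indicator of whether treatment is working, "correlate circulating DNA levels with tumor imaging of metastases", and finally "We will utilize this assay to measure circulating tumor DNA and correlate changes in DNA levels with response to treatment".
- **Section 2.4.3 (prior evidence):** in the cited assay study, "the level of ctdDNA strongly and significantly correlated with tumor burden as assessed by cross sectional imaging". No coefficient is given.
- **Section 13.5 (analysis):** "An additional exploratory objective is to assess whether circulating tumor DNA can be detected", followed by "If so, these numeric data will be summarized by clinical response". It names no change measure, time point, imaging variable or method of association for ctDNA.

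The data for the wider aims are scheduled. On sampling, section 2.4.3 says "All patients will undergo blood collection on a monthly basis for analysis of circulating tumor DNA levels"; section 9.2.3 and Study Calendar footnote l place the draws before treatment, at the start of each cycle and at end of treatment. Scans are every 8 weeks (footnote g). Under section 11.1.2 the sum of diameters "for all target lesions will be calculated and reported as the baseline sum diameters", and section 11.1.4.1 judges later change against it.

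**The concern.** Both variables are numeric and measured repeatedly. Reducing tumour change to a response category before relating it to ctDNA discards part of what was measured, and 13.5 never uses the on-treatment ctDNA trajectory.

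Categories may also be coarse in this disease. Section 2.2.1.2 reports no radiographic response among 16 uveal melanoma patients on phase I trametinib, although 2 had a 24% reduction. Section 2.3.3 reports 15% partial responses on selumetinib while half of the patients had some shrinkage.

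At stake is whether the ctDNA objective can be answered as set. Without a stated method, the time point, change measure and grouping would be chosen after the data are seen.

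**Working it through.** **The plan's own figure.** There is none for ctDNA. The only power statement in section 13 concerns PFS and does not bear on this point.

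**Aims against analysis**

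| Aim (1.3, 2.4.3) | In 13.5? |
|---|---|
| Change with therapy; evolution of levels | No |
| Early change as an indicator of effect | No |
| Levels against imaging | No |
| Changes against response | Partly: levels summarised by response, change not named |

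**Inputs for the size**

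- n = 40: the per-arm figure in 13.1, and the number to which a continuing arm may accrue.
- Responders: 7/46 = 15.2% on selumetinib (2.3.3), so 40 × 7/46 = 6.1, taken as 6. The exact 95% interval for 7/46 is 6.3% to 28.9%. This rate is borrowed from another drug.
- Correlation ρ between ctDNA change and tumour change: not in the documents. Assumed 0.4, 0.5 and 0.6.

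**Information kept after grouping** (bivariate-normal model, relative to continuous tumour change)

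- Responder split at p = 0.15: φ(z)²/[p(1−p)], with z = −1.036 and φ(z) = 0.2332, gives 0.0544/0.1275 = 0.43.
- Three ordered categories: Σ pⱼmⱼ², where mⱼ is the mean normal score in category j. PR/SD/PD shares of 15/50/35% give 0.79, 15/35/50% give 0.76, and 15/25/60% give 0.71.

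**Simulated power** (two-sided 5%, n = 40, 6 responders). The methods are Spearman on continuous change, a rank-sum test for the responder split, and Spearman on ordered categories. Figures in brackets are from a repeat of 2,500 runs with shares of 15/35/50%.

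| ρ | Continuous | Responder split | Ordered PR/SD/PD |
|---|---|---|---|
| 0.4 | 70% (70%) | 37% (34%) | 61% (59%) |
| 0.5 | 89% (89%) | 52% (50%) | 82% (78%) |
| 0.6 | 98% (98%) | 72% (69%) | 95% (94%) |

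Points lost:

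- Responder split: 70−37 = 33, 89−52 = 37, 98−72 = 26.
- Ordered categories: 70−61 = 9, 89−82 = 7, 98−95 = 3. In the repeat: 11, 11 and 4.

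As a check on the continuous column, Fisher's approximation Φ(√37 · atanh ρ − 1.96) gives 73%, 92% and 99%, slightly above Spearman as expected.

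**Sensitivity.** With only 5% responders, power for the split is 14%, 24% and 33%. With 60 patients (the figure in 13.2) and 9 responders, power at ρ = 0.4 is 87% continuous, 51% split and 78% ordered.

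**The case against.** **No test is planned, so no power is lost.** This stands as far as it goes. 13.5 speaks of a summary, labels the correlative work exploratory, and sets no alpha or power for ctDNA. The power figures therefore show how much of the data each method would use; they do not measure a shortfall against a plan. But 2.4.3 says these quantities will be correlated, and that needs a method.

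**Section 2.4.3 already commits to the analyses.** It does, and a brief 13.5 does not cancel it. It still gives no time point, scale or statistic, and the analysis section should.

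**Response need not be binary.** A reader might infer that 13.5 compares responders with everyone else and so discards most of the power. The documents do not support that. 13.5 attaches CR+PR to the response rate, not to clinical response. It applies a rank-sum test to clinical response by mutation status, which fits ordered categories, and 13.6.2 assigns separate categories. Fisher's exact test in the same section points the other way, so the meaning is open. On the ordered reading little is lost, and a 25% shrinkage would not share a group with progression. Even for a binary split, more than half the power goes only when the correlation is weak (43% to 18% at ρ = 0.3; about half at 0.4) or responders are very few.

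**The response threshold is not arbitrary.** A reader might infer that the 30% cut lacks a source. Section 11.1 adopts RECIST 1.1 with a reference, and 11.1.4.1 states the threshold under it.

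**The model favours the continuous measure.** This stands in part. The cited study relates ctDNA level to tumour burden, not change to change. Percent change in target lesions also misses new lesions, non-target progression and early death, so the fix must provide for them.

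**Conclusion.** The gap holds as one of analysis choice: 13.5 omits the imaging-correlation and early-change analyses that 1.3 and 2.4.3 call for, and leaves the grouping undefined. A responder split would keep about 43% of the information in continuous tumour change, a loss of 26 to 37 points of power over ρ = 0.4 to 0.6. Ordered categories lose about 3 to 9 points, up to 11 if half the patients progress.

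These sizes rest on an assumed correlation, a bivariate-normal model with complete data, one arm of 40, and a response rate taken from selumetinib. It would be too strong to say that a real relation would probably be missed: at ρ = 0.5 or above, even the split has power of about one half or more. The primary analysis is untouched. This is an optional improvement to an exploratory analysis.

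**What to change.** Add to 13.5:

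- **Main ctDNA analysis.** Spearman rank correlation, stratified by arm and with a 95% confidence interval, of change in ctDNA from baseline to the start of cycle 2 and of cycle 3 with percent change in the sum of target-lesion diameters at the week-8 scan. Cycle 2 starts at week 5, so it addresses early change; cycle 3 starts at week 9 and is roughly concurrent with the scan.
- **Undetectable ctDNA.** A value that becomes undetectable on treatment takes the lowest rank. Patients undetectable at baseline have no fall to rank and are reported separately. At the 20 of 21 detected in the study cited in 2.4.3, that is about 2 of 40 (40 × 1/21 = 1.9).
- **Imaging.** Progression by new or non-target lesions, or death before the scan, takes the worst imaging rank. Report how many patients lack a ctDNA sample or a scan for other reasons.
- **Response.** State that clinical response means the RECIST categories, and keep the summary by category as descriptive.
- **Optional.** Relate cycle-2 change to later PFS among patients progression-free at that landmark.

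The cost is a few sentences of SAP text and a few lines of code. No patient, visit, scan or assay is added.
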